4.7.3. Secondary analyses

Similar to the primary analyses, univariate analyses of PFS and OS for subgroups (age and comorbidity) of all mBC patients having palbociclib + AI as first-line treatment will be made and with the same definitions and timelines for their estimation.

These subgroups of HR+/ HER2 negative mBC patients are:

Age-groups

- Patients below 65 years of age
- Patients 65-74 years of age
- Patients 75+ years of age

Statistical test of differences in baseline characteristics as well as the PFS and the OS outcomes between each of these age subgroups compared to all first-line palbociclib patients the Shapiro-Wilk test of normality and the Wilcoxon rank sum will be applied.

Palbociclib

A5481188 NON-INTERVENTIONAL STUDY STATISTICAL ANALYSIS PLAN FOR SECONDARY DATA

COLLECTION STUDY

Version 1.0, 1 March 2024

PFIZER CONFIDENTIAL

CT24-WI-GL03-RF03 3.0 *Non-Interventional Statistical Analysis Plan*
for Secondary Data Collection Study

Page 9 of 15

Comorbidities as measured by Charlson Comorbidity Index (CCI)

- Patients split by comorbidity severity score (CCI; 0, 1, 2, and 3 or higher (3+))
- Patients split by number of comorbidities (0, 1, 2+)
- Patients split in types of comorbidities (Cardiac disease, Vascular disease, Metabolic disease, Psychiatric disease, Blood and lymphatic system)

Statistical test of differences in baseline characteristics as well as the PFS and the OS outcomes between each of these comorbidity groups will be performed, e.g. using the chi-square test).

And finally various disease-specific characteristics of the mBC patients having palbociclib + AI as first-line treatment.

- Patients with or without visceral disease
- Bone only patients
- Endocrine resistant, endocrine sensitive or de novo patients

Similar statistical test of difference as for the two other subgroups will be made for the disease-specific characteristics.

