4.7. Statistical methodology and analyses

The study is a single-arm study and will be purely descriptive and explorative. No formal hypotheses will be tested.

This study will provide two types of outcomes:

1. Outcomes on PFS and OS of patients treated with palbociclib+AI as first-line (population and subpopulations (Age and Comorbidity) (Appendix A, Table 3 and 4))
2. Descriptive statistics on the population/subpopulations treated with palbociclib+AI (Appendix A, Table 1 and 2)

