4.7.1. Index date and follow-up

Definitions of the incidence data and the index date of the first-line treated palbociclib + AI patients shown together with the definition of the treatment outcomes (PFS and OS), as well as definition of visceral disease can be found in the table below.

Incidence date	The date of the initial breast cancer diagnosis.
Index date	The date of relapse or stage IV disease.
Progression Free Survival (PFS)	The time from the date of relapse or stage IV disease (index date) to progression or death, whichever occurs first. Patients will be censored 31 December 2021. Progression is based on radiological, clinical, and biochemical examination from the treating departments.
Overall Survival (OS)	The time from index date to death at any cause.
Visceral disease	Defined as metastases in the organs, e.g., lung, liver. Visceral disease is based on the variable Location of metastases (RE10-18 + 80-81, 117-119, 219-222) in the DBCG database.

For the PFS and OS outcomes for the full palbociclib first-line population (primary analyses) as well as each subpopulation (secondary analyses), as presented below, Kaplan-Meier survival distribution functions with 95% confidence intervals will be estimated. Hence, if possible median PFS and OS as well as interquartile ranges (IQR) will be estimated. Unadjusted Kaplan Meier curves will be presented to illustrate time-to-event (PFS or OS).

For the descriptive statistics, numbers and percentages will be provided and presented in tables, including cross tabulations (see section 6 for presentation of tables shells).

All data analysis will be executed using the statistical software R-studio.

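### SAP 4.7.3 compares PFS and OS with rank-sum and chi-square tests that ignore censoring, and tests each age group against a cohort that contains it

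*SAP*

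**What the plan says.** SAP 4.7.3 announces, for the age groups, a "Statistical test of differences in baseline characteristics as well as the PFS and the OS outcomes". The same sentence then gives the comparator and the method: "compared to all first-line palbociclib patients the Shapiro-Wilk test of normality and the Wilcoxon rank sum will be applied". One sentence therefore covers both baseline variables and the two time-to-event outcomes.

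For the three comorbidity splits (CCI score, number and type), the same kind of test "between each of these comorbidity groups will be performed, e.g. using the chi-square test". For visceral, bone-only and endocrine-status groups, "Similar statistical test of difference as for the two other subgroups will be made for the disease-specific characteristics".

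Estimation is handled differently. SAP 4.7.1 states that "Kaplan-Meier survival distribution functions with 95% confidence intervals will be estimated", for the full population and for each subpopulation. SAP 4.7 also says "No formal hypotheses will be tested". Neither document names a log-rank test, a censored-data Wilcoxon test or a Cox model, and neither gives a significance level.

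**The concern.** There are four faults, the first two being the main ones.

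1. **Censoring.** Patients start treatment over five years and are cut off on one date, so many have no event by then. Ranking observed times treats a patient censored at 30 months like one who died at 30 months. Chi-square on event status ignores how long each patient was at risk. Neither tests equality of survival curves, and a normality test has no role for censored times.
2. **Overlap.** The rank-sum test assumes two independent samples. A subgroup set against all patients appears in both.
3. **Comorbidity types are not disjoint.** Protocol 9.4 allows several comorbidities per patient, so one person can count as both cardiac and metabolic. A chi-square between types fails on independence, and that split has no reference group.
4. **Inconsistency.** Tests are specified in a plan that says no hypotheses will be tested.

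Age and comorbidity are the question in the study title, and SAP 4.7.3 holds its only formal between-group comparisons. Followed literally, the plan could miss real differences, or report differences that reflect only when a subgroup's patients began treatment.

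**Working it through.** The documents give no alpha, effect size or power, so there is no design figure to reproduce. Protocol 9.8 gives a maximum follow-up of 7 years and one month. That checks: 1 January 2017 to 1 February 2024 is 85 months.

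**Inputs from the documents**
- 580 patients (SAP 4.5), treatment started 1 January 2017 to 31 December 2021 (SAP 4.2).
- Cut-off 31 December 2023 (SAP 4.7.2) or 1 February 2024 (Protocol 8.1), so potential follow-up from treatment start is about 24 to 84 or 25 to 85 months. SAP 4.7.1 also gives 31 December 2021 for PFS.
- Median OS 56.9 and PFS 31.3 months, from the earlier Danish registry study (Protocol section 7; endocrine-sensitive AI group).

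**Assumptions not in the documents**
- Exponential survival, uniform entry and two-sided 5% tests.
- Subgroup share *f* of 0.2 to 0.5.
- Hazard ratios and entry patterns as stated below.

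**Step 1: how much censoring?** With λ = ln 2 / median and follow-up uniform on (a, b), the censored fraction is (e^(−λa) − e^(−λb)) / (λ(b − a)).
- OS, 24 to 84 months: λ = 0.01218, so (0.7465 − 0.3594) / 0.731 = 0.53. About 273 of 580 have an event.
- PFS, 24 to 84 months: λ = 0.02215, so (0.588 − 0.156) / 1.329 = 0.325. About 391 have an event.
- At the protocol cut-off the censored fractions are 52% and 32%. With the 31 December 2021 date, PFS censoring would be 55%.

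**Step 2: overlap alone.** The subgroup mean minus the overall mean equals (1 − f) times the subgroup mean minus the mean of the rest.
- True variance: σ²(1 − f)/(fN).
- Variance assumed for independent samples: σ²(1 + f)/(fN).
- The z statistic is therefore shrunk by √((1 − f)/(1 + f)).
- f = 0.2: √(0.8/1.2) = 0.816. Then 1.96/0.816 = 2.40, and the true size is 1.6%.
- f = 0.4: √(0.6/1.4) = 0.655. Then 1.96/0.655 = 2.99, and the true size is 0.3%.

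**Step 3: power.** Simulation with 580 patients, SAP cut-off, hazard ratio 1.5, same entry pattern in both groups, 1,500 to 2,000 runs per setting (% rejected):

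| Outcome, f | Rank-sum vs all (planned) | Rank-sum vs rest | Chi-square on status | Log-rank vs rest |
|---|---|---|---|---|
| OS, 0.2 | 50.7 | 68.5 | 76.5 | 83.3 |
| OS, 0.35 | 47.5 | 79.9 | 89.5 | 92.6 |
| OS, 0.5 | 35.8 | 84.8 | 90.5 | 93.8 |
| PFS, 0.2 | 71.3 | 85.2 | 81.4 | 92.2 |
| PFS, 0.35 | 77.5 | 94.0 | 92.0 | 97.4 |
| PFS, 0.5 | 61.0 | 96.1 | 94.0 | 98.4 |

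For OS at f = 0.2, ignoring censoring costs 83.3 − 68.5 = 14.8 points, and overlap a further 68.5 − 50.7 = 17.8. As a check, the Schoenfeld formula with 273 events gives √(273 × 0.2 × 0.8) × ln 1.5 − 1.96 = 0.72, or 76% for log-rank. That is a little below the simulation, because 273 is the event count without the subgroup's higher hazard.

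A second simulation (protocol cut-off, 1,000 runs) agrees: 54% against 85% for OS hazard ratio 1.5 at f = 0.2, and 47% against 95% at f = 0.4. For PFS hazard ratio 1.3 it gives 29% against 58%, and 25% against 74%.

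**Step 4: false positives when entry differs.** Hazard ratio 1, OS, f = 0.2. The late share is the proportion of the subgroup entering in the second half of accrual; it is 50% in the rest (% rejected):

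| Late share | Rank-sum vs all | Rank-sum vs rest | Chi-square | Log-rank |
|---|---|---|---|---|
| 50% | 1.5 | 4.5 | 4.3 | 4.7 |
| 65% | 7.2 | 15.4 | 9.6 | 5.4 |
| 80% | 34.2 | 52.7 | 18.8 | 5.5 |

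If subgroup entry instead starts 12 or 24 months later (protocol cut-off), the planned rank-sum rejects 9.0% or 50.1%, chi-square 9.5% or 30.6%, and log-rank 4.6% or 5.5%.

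**The case against.** The strongest reply is that the damage is confined. The primary objectives are whole-cohort PFS and OS. All medians, curves and confidence intervals come from Kaplan-Meier, which handles censoring. The shells for Tables 3 and 4 have no p-value column, and the study calls itself descriptive. All of this stands: the fault lies only in the secondary subgroup tests. But SAP 4.7.3 still commits to those tests.

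Other points, and what remains of each:

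- **Chi-square is only an example**, and might loosely mean a log-rank statistic. The SAP does not say so, and it uses the same sentence for baseline characteristics. Pairing Wilcoxon with a normality test points to the ordinary rank-sum.
- **The error is mostly conservative.** True for the planned age comparison when entry patterns are alike. In a separate run for OS, rejection under no difference was 2.1%, 2.4% and 5.1% for entry delays of 3, 6 and 9 months at f = 0.2, and lower at f = 0.4. For PFS it was 2.6% at 12 months and 8.1% at 24 (f = 0.2). Real inflation needs entry to differ by about a year or more, and the documents give no entry dates by subgroup. Under smaller differences the cost is lost power.
- **Chi-square loses little power.** Also true with equal entry (76.5% against 83.3% for OS at f = 0.2). Its weakness is false positives when entry differs.
- **A comorbidity-free group exists** as CCI 0 and as zero comorbidities. It is missing only from the split by type.
- **Exploratory p-values can coexist with no formal hypotheses.** Fair; this is the weakest of the four faults.

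**Conclusion.** The concern holds: the outcome tests in SAP 4.7.3 are wrong as written. They ignore censoring that is likely to affect about half of OS times and a third of PFS times, and the age comparisons use overlapping samples. Overlap invalidates the stated significance level at any subgroup size, making it about 1.6% instead of 5% at a 20% share.

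The practical loss for OS at hazard ratio 1.5 is from about 83% power to 51% at a 20% share, and more in larger subgroups. False positives rise only if subgroups differ in when they entered: up to about 50% for OS with a 24-month delay, where log-rank holds near 5%.

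The power and false-positive figures rest on exponential survival, medians from one earlier study, follow-up counted from treatment start, and assumed shares, effects and entry patterns. The finding that the tests do not suit the endpoints needs none of these assumptions.

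**What to change.** Rewrite the testing sentences in SAP 4.7.3 so that outcomes and baseline variables are treated separately.

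- **PFS and OS:** log-rank tests and Cox hazard ratios with 95% confidence intervals between mutually exclusive groups. Compare 65-74 and 75+ with under 65; CCI 1, 2 and 3+ with 0; one and two or more comorbidities with none.
- **Comorbidity type:** presence versus absence, separately for each of the five types.
- **Disease-specific groups:** the same approach, between disjoint categories.
- **Baseline variables:** keep rank-sum and chi-square, between disjoint groups only.
- Drop Shapiro-Wilk and the comparison with all patients for outcomes, and label every p-value exploratory.

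The log-rank test on disjoint groups is enough to cure the fault; the Cox model adds an effect size. Dropping the outcome tests and reporting subgroup Kaplan-Meier estimates with confidence intervals would also cure it, and would fit the descriptive aim.

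The cost is SAP wording and standard survival procedures, with no extra data. The SAP needs revision anyway: its two PFS censoring dates conflict with each other and with protocol version 3.0, and any outcome test depends on that date.

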6. APPENDICES

6.1. Appendix A: Table shells

This section presents an overview of the table shells.

Table 1. Descriptive statistics. All mBC patients having palbociclib as first-line treatment in combination with AI

Population	Subgroup	Outcome	Result
All included patients (first-line treated with palbociclib+AI)	All patients	Number of patients (all)	N (100%)
		Age	Median, mean and standard deviation
All included patients (first-line treated with palbociclib+AI)	Patients below 65 years of age	Number of patients	N (%)
	Patients 65-74 years of age	Number of patients	N (%)
	Patients 75+ years of age	Number of patients	N (%)
All included patients (first-line treated with palbociclib+AI)	Comorbidities 1 - patients split into severity of comorbidities as measured by CCI (0, 1, 2, 3 or higher (3+))	Number of patients with a CCI score of 0, 1, 2, 3 or higher (3+), respectively	N (%) in each group
		Age	Median, mean and standard deviation
	Comorbidities 2 - patients split into number of comorbidities (0, 1, 2+)	Number of patients with 0, 1, or 2+ comorbidities, respectively	N (%) in each group
		Age	Median, mean and standard deviation
	Comorbidities 3 - patients split into type of comorbidities (Cardiac disease, Vascular disease, Metabolic disease, Psychiatric disease, Blood and lymphatic system)	Number of patients with specific type of comorbidity	N (%) in each group
		Age	Median, mean and standard deviation
All included patients (first-line treated with palbociclib+AI)	Patients with visceral disease	Number of patients	N (%)
		Age	Median, mean and standard deviation
	Patients without visceral disease	Number of patients	N (%)
		Age	Median, mean and standard deviation
All included patients (first-line treated with palbociclib+AI)	Patients bone only	Number of patients	N (%)
	Age	Median, mean and standard deviation	
	Endocrine resistant patients	Number of patients	N (%)

		Age	Median, mean and standard deviation
Endocrine sensitive patients	Number of patients	N (%)	
		Age	Median, mean and standard deviation
De Novo patients (primary mBC)	Number of patients	N (%)	
		Age	Median, mean and standard deviation

Table 2. Disease-specific descriptive statistics. All mBC patients having palbociclib as first-line treatment in combination with AI

Population	Subgroup	Outcome	Result

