All included patients (first-line treated with palbociclib+AI)	All patients	Type of metastases	Visceral: N (%) Non-visceral: N (%) Both: N (%)
		Number of metastases	0: N (%) 1: N (%) 2: N (%) >2: N (%)
		Metastatic site	Skin: N (%) Bone: N (%) Lung: N (%) Liver: N (%) CNS: N (%) Other: N (%)
	Patients below 65 years of age	Type of metastases	Visceral: N (%) Non-visceral: N (%) Both: N (%)
		Number of metastases	0: N (%) 1: N (%) 2: N (%) >2: N (%)
		Metastatic site	Skin: N (%) Bone: N (%) Lung: N (%) Liver: N (%) CNS: N (%) Other: N (%)
	Patients 65-74 years of age	Type of metastases	Visceral: N (%) Non-visceral: N (%) Both: N (%)
		Number of metastases	0: N (%) 1: N (%) 2: N (%) >2: N (%)
		Metastatic site	Skin: N (%) Bone: N (%) Lung: N (%) Liver: N (%) CNS: N (%) Other: N (%)
	Patients 75+ years of age	Type of metastases	Visceral: N (%) Non-visceral: N (%) Both: N (%)

All included patients (first-line treated with palbociclib+AI)	Comorbidities 1 - patients split into severity of comorbidities as measured by CCI (0, 1, 2, 3 or higher (3+))	Number of metastases	0: N (%) 1: N (%) 2: N (%) >2: N (%)
		Metastatic site	Skin: N (%) Bone: N (%) Lung: N (%) Liver: N (%) CNS: N (%) Other: N (%)
		Type of metastases	Visceral: N (%) Non-visceral: N (%) Both: N (%)
		Number of metastases	0: N (%) 1: N (%) 2: N (%) >2: N (%)
		Metastatic site	Skin: N (%) Bone: N (%) Lung: N (%) Liver: N (%) CNS: N (%) Other: N (%)
		Type of metastases	Visceral: N (%) Non-visceral: N (%) Both: N (%)
		Number of metastases	0: N (%) 1: N (%) 2: N (%) >2: N (%)
		Metastatic site	Skin: N (%) Bone: N (%) Lung: N (%) Liver: N (%) CNS: N (%) Other: N (%)
		Type of metastases	Visceral: N (%) Non-visceral: N (%) Both: N (%)
		Number of metastases	0: N (%) 1: N (%) 2: N (%) >2: N (%)
		Metastatic site	Skin: N (%) Bone: N (%) Lung: N (%) Liver: N (%) CNS: N (%) Other: N (%)
		Type of metastases	Visceral: N (%) Non-visceral: N (%) Both: N (%)
		Number of metastases	0: N (%) 1: N (%) 2: N (%) >2: N (%)
		Metastatic site	Skin: N (%) Bone: N (%) Lung: N (%) Liver: N (%) CNS: N (%) Other: N (%)

Table 3. Progression Free Survival (PFS)*. All mBC patients having palbociclib as first-line treatment in combination with AI

Endpoint	Population	Subgroup	Outcome	Result
Primary	All included patients (first-line treated with palbociclib+AI)	All patients	PFS	Median and IQR
Secondary	All included patients (first-line treated with palbociclib+AI)	Patients below 65 years of age	PFS	Median and IQR

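### SAP 4.7.3 tests baseline differences by age group with methods that do not fit the categorical items tabulated, compares each age group with a whole that contains it, and names no test for age by comorbidity group

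*SAP*

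**What the plan says.** SAP 4.7.3 sets out three groups of comparisons.

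- **Age groups.** Differences in baseline characteristics, PFS and OS are tested "between each of these age subgroups compared to all first-line palbociclib patients", and for this "the Shapiro-Wilk test of normality and the Wilcoxon rank sum will be applied". This is a firm instruction, not an example.
- **Comorbidity groups.** A test of differences in the same three things "between each of these comorbidity groups will be performed, e.g. using the chi-square test". Here the test is only an example.
- **Disease-specific groups.** "Similar statistical test of difference as for the two other subgroups will be made for the disease-specific characteristics". No test is named, and the two sets it points to use different ones.

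The shells in SAP Appendix A show what would be tested at baseline. By age group, Table 1 gives only the number and percentage of patients. Table 2 gives type of metastases ("Visceral: N (%) Non-visceral: N (%) Both: N"), number of metastases (0, 1, 2, more than 2) and metastatic site ("Skin: N (%) Bone: N (%) Lung: N (%) Liver: N (%) CNS: N (%) Other: N"). By comorbidity group, Table 1 also gives age as "Median, mean and standard deviation", and Table 2 repeats the metastasis items for the CCI-score groups.

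SAP 4.5 and 4.7 describe the study as descriptive and explorative, without formal hypotheses. No significance level is given, and no rule links the test to the type of variable.

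**The concern.** This point concerns the baseline comparisons only, although the same sentences also cover PFS and OS.

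The tests named for the age groups are meant for continuous or at least ordered data, and nothing baseline in the age-group shells is continuous. Age is the one continuous item in the shells, and it defines those groups. On the comorbidity side age is a proper baseline variable, but the only test mentioned there does not handle it as a continuous measure. In addition, each age group is compared with the full cohort, of which it is a part.

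The survival curves are unadjusted (SAP 4.7.1), so readers will look to the baseline comparison to judge whether age or comorbidity groups differ in disease burden. An analyst would have either to follow an instruction that gives an arbitrary p-value or to choose another test after seeing the data.

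**Working it through.** The plan states no figure to reproduce. The check matches each test to the shelled items and then illustrates the consequences. The total of 580 is from SAP 4.5; all other counts and shares are assumptions.

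**1. Test against item, by age group**

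| Item (Table 2) | Scale | Shapiro-Wilk | Rank-sum |
|---|---|---|---|
| Type of metastases | three unordered classes | no use | depends on coding |
| Number of metastases | ordered | no use | valid in form |
| Site, as one six-class item | unordered | no use | depends on coding |
| Site, each as yes/no | binary | no use | close to chi-square |

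Shapiro-Wilk checks normality. It does not test a difference between groups on any of these items.

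**2. Coding dependence for metastasis type.** Assume 200 against 380 patients, with counts 80/60/60 and 120/160/100 in the shell order (visceral, non-visceral, both).

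- Chi-square on 2 df: 8.40, p = 0.015.
- Rank-sum, classes numbered in shell order: p = 0.44.
- Rank-sum, non-visceral lowest, then visceral, then both: p = 0.020.
- Rank-sum, visceral lowest, then both, then non-visceral: p = 0.0056.

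Reversing an order leaves p unchanged, so these are all the possible values. The data are identical in each case.

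**3. A yes/no item.** Assume 60 of 200 against 150 of 380. Chi-square is 5.092 (p = 0.0240). The squared rank-sum statistic is (N − 1)/N × chi-square = 579/580 × 5.092 = 5.083 (p = 0.0242). The two tests practically coincide.

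**4. Subgroup against all patients.** Let the subgroup hold a share s = n₁/N. The rank-sum test treats the samples as independent and assumes a variance proportional to 1/n₁ + 1/N. Because the whole contains the subgroup, the true variance is proportional to 1/n₁ − 1/N. Assumed over true is (1 + s)/(1 − s). A nominal two-sided 0.05 test therefore rejects only when a standard normal exceeds 1.96 × √[(1 + s)/(1 − s)] in absolute value.

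| s | n₁ | Effective cut-off | Type I error, formula | Simulated, against all | Simulated, against the rest |
|---|---|---|---|---|---|
| 0.20 | 116 | 1.96 × √1.500 = 2.40 | 0.016 | 0.015 | 0.050 |
| 0.35 | 203 | 1.96 × √2.077 = 2.82 | 0.0047 | 0.005 | 0.049 |
| 0.45 | 261 | 1.96 × √2.636 = 3.18 | 0.0015 | 0.002 | 0.051 |

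The simulation used 4,000 runs with no true difference, on a four-level ordered item with assumed probabilities of 5%, 45%, 30% and 20%. The fault comes from the comparator, so replacing rank-sum by another two-sample test would not remove it.

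**5. Comorbidity groups.** Chi-square suits the Table 2 items in form. It does not compare age as a continuous variable, and no other test is mentioned. Patients can have more than one type of comorbidity, so the five types are not independent groups. Sparse cells are possible: if CCI 3+ held 20 patients (20/580 = 3.4%) and a site occurred in 3% to 10%, expected counts would be 20 × 0.03 = 0.6 to 20 × 0.10 = 2.0. At 10% prevalence the expected count stays below 5 for any group under 50 patients (50/580 = 8.6%). The documents give no size for this group.

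**The case against.** The strongest reply is that little depends on these p-values. The study tests no formal hypothesis, the p-values gate no other analysis, and the tabulated counts and percentages, which tell a reader most about imbalance, are correct whatever test follows. That stands, and it limits the weight of the point.

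Three further replies also stand in part.

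- A reader might infer that rank-sum is wrong for every item because all are categorical. It is not. Number of metastases is ordered, and for yes/no sites rank-sum gives almost the chi-square p-value. The clear mismatch is metastasis type, plus site if it is analysed as one multi-class item. One could argue that type has an order by disease burden, but the SAP states none, and step 2 shows that the choice matters.
- A reader might infer that the SAP prescribes chi-square for age by comorbidity group. It does not. Chi-square is an example, and it is appropriate for the metastasis items in those groups. For age the fault is that no test is specified.
- A reader might infer that chi-square is shown to fail for CCI 3+. The sparse-cell figures rest on assumed sizes. They justify an exact-test fallback and nothing more.

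The SAP does not say that baseline testing is confined to the shelled items. The wider variable list in SAP 4.3 includes ordered items, such as CCI score, that a rank test would suit. It also includes unordered ones, such as endocrine status, that it would not. So the need for a rule by variable type remains.

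**Conclusion.** The point holds in a limited form. For age groups, SAP 4.7.3 firmly prescribes a normality check that tests no difference, and a rank test whose result on metastasis type is arbitrary (0.44, 0.020 or 0.0056 for the same assumed counts). It applies them to a comparison of part with whole that lowers a nominal 0.05 to about 0.002 to 0.015 for assumed shares of 20% to 45%. The overlap is the more serious fault: it affects every item, including those for which rank-sum is otherwise acceptable, and it hides real differences between age groups. For comorbidity groups the fault is incomplete specification: age has no named test.

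The effect is confined to the baseline p-values. A reader might infer that the primary results are at risk; they are not, because the Kaplan-Meier estimates of PFS and OS use none of these tests. This is a minor correction, worth making because it costs little.

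**What to change.** Rewrite the test sentences in SAP 4.7.3 so that baseline tests are stated separately from outcome tests.

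- Compare the three age groups with each other, not with all patients.
- Metastasis type, and each site as its own yes/no item: chi-square, or Fisher's exact test when any expected count is below 5.
- Number of metastases: Kruskal-Wallis.
- Age across CCI-score groups and across number-of-comorbidity groups: Kruskal-Wallis.
- Types of comorbidity: compare patients with and without each type, choosing the test by variable type as above.
- Disease-specific groups: apply the same rule between non-overlapping groups.
- Do not test age across age groups, and delete the Shapiro-Wilk step.

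Reporting no baseline p-values at all would also be consistent with the descriptive aim, if the sponsor prefers that.

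The cost is one short paragraph in the SAP and no new data. If baseline tables already carry p-values, only those need rerunning. The change touches no primary endpoint definition or analysis, so under Protocol 9.8 a SAP revision should be enough.

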## 9. RESEARCH METHODS

### 9.1. Study Design

The study is designed as a secondary data collection NI-Study. Retrospective data will be collected from an existing registry - the DBCG registry. The focus of this study will be on HR+/HER2- locally advanced or metastatic breast cancer treated with palbociclib. The study is a single-arm study focusing on patients treated with palbociclib in Denmark.

The study is purely descriptive and explorative. No formal hypotheses will be tested in the study.

Since the establishment in 1976, the DBCG has maintained a clinical registry for early breast cancer patients in Denmark in which surgeons, pathologists, medical geneticists and oncologists report data regarding diagnosis, treatment and follow-up of breast cancer (39,40). This is a unique clinical registry. This well-established breast cancer registry (1976) managed by DBCG was expanded in 2017 to include retrospective and prospective clinical and pathological data on breast cancer patients with a relapse. This includes both the primary mBC (De Novo) and recurrent mBC.

The DBCG registry focusing on relapses on which the study will be based is one of several DBCG registries. All Danish patients with locally advanced or metastatic breast cancer are included in the DBCG registry. The data and records in the registry are based on systematic review following a standard case report form of all electronic patient records of patients diagnosed with locally advanced or metastatic breast cancer.

PFIZER CONFIDENTIAL

The data collection and the ongoing populating of the DBCG registry are performed by healthcare professionals in the DBCG secretariat and are conducted independently of this study. Compared to other exhaustive national Danish patient registries, the DBCG registry contains detailed clinical and pathological data about the treatment patterns of patients with HR+/HER2- locally advanced or metastatic breast cancer. Thus, the registry is an important and well-suited source to address the research questions of the present study and has previously been used to analyze treatment outcomes for all first- and second-line palbociclib patients in Denmark (29).

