4.5. Sample size and power calculations

The study is purely descriptive and explorative. No formal hypotheses will be tested in the study. Calculation of sample size is therefore not applicable.

The expected and estimated total study population with the focus on all Danish mBC patients (endocrine sensitive, endocrine resistant or de novo) that have received palbociclib in combination with AI as first-line therapy. 580 patients will be included from 1 January 2017 to 31 December 2021.

Subgroup analyses of this patient population will be made based on age and comorbidity.

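### SAP 4.7.3 orders some 14 to 54 uncorrected PFS and OS subgroup tests in a study declared purely descriptive, with no alpha, test count, pairwise-or-overall rule or nominal label

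*SAP*

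**What the plan says.** Protocol 9.1: "The study is purely descriptive and explorative. No formal hypotheses will be tested in the study". SAP 4.7 repeats this, and SAP 4.5 draws a consequence from it: "No formal hypotheses will be tested in the study. Calculation of sample size is therefore not applicable".

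SAP 4.7.3 then gives three test instructions, each covering baseline characteristics as well as PFS and OS.

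- **Age groups:** the tests are "between each of these age subgroups compared to all first-line palbociclib patients the Shapiro-Wilk test of normality and the Wilcoxon rank sum will be applied".
- **Comorbidity groups** (CCI score, number, type): tests of "the PFS and the OS outcomes between each of these comorbidity groups will be performed", with chi-square as an example.
- **Visceral, bone-only and endocrine groups:** "Similar statistical test of difference as for the two other subgroups will be made for the disease-specific characteristics".

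The result column of Tables 3 and 4 (SAP Appendix A) holds only the median and interquartile range. Those tables label the visceral, bone-only and endocrine rows Secondary. The secondary objectives in protocol section 8 and SAP 3.2 cover only age and comorbidity.

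**The concern.** The title of the study promises the impact of age and comorbidities on outcomes, and protocol section 12 plans a journal article. Its conclusions will therefore be about which groups differ. The SAP asks for many tests to support such statements but does not say how many, at what level, against which comparator, or how a p-value is to be read. With no place for them in the shells, there is also no rule on which ones get reported.

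Two groupings overlap heavily. Protocol 9.4 defines a CCI score of 0 as no comorbidity and derives the number of comorbidities from the CCI. One chance pattern can then appear in both groupings and look like corroboration.

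The problem is separate from the choice of test. Replacing Wilcoxon and chi-square with a log-rank test would leave it unchanged.

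**Working it through.** **Inputs.** Neither document gives an alpha, a power or a test count, so there is no plan figure to reproduce. The 580 patients in SAP 4.5 are an expected registry count. Group numbers come from SAP 4.7.3: age 3, CCI 4, number of comorbidities 3, type 5, visceral 2, endocrine 3. Bone-only has 2 groups, since Tables 3 and 4 carry the complement row. There are two endpoints. A two-sided 0.05 is an assumption; the only level stated is 95% for the Kaplan-Meier intervals (SAP 4.7.1).

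**Step 1: count the tests.** With k(k-1)/2 pairs per grouping: 3 + 6 + 3 + 10 + 1 + 1 + 3 = 27 contrasts, and 27 x 2 = 54. Age contributes 3 either way, because comparing each group with all patients also gives three contrasts. The SAP wording allows smaller counts:

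- One overall test per grouping: 7 x 2 = 14.
- The same, with each comorbidity type tested as present or absent: (6 + 5) x 2 = 22.
- Age groups each against all, other groupings overall, types present or absent: (3 + 5 + 5) x 2 = 26.
- Pairwise (age groups each against all), types present or absent: (3 + 6 + 3 + 5 + 1 + 1 + 3) x 2 = 44.

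**Step 2: false positives when no true difference exists.** Expected number = 0.05m. Chance of at least one, if independent = 1 - 0.95^m.

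| Tests (m) | Expected | Independent | Simulated |
|---|---|---|---|
| 14 | 0.7 | 51% | about 45% |
| 22 | 1.1 | 68% | 59-60% |
| 26 | 1.3 | 74% | not run |
| 44 | 2.2 | 90% | 71-72% |
| 54 | 2.7 | 94% | 81-82% |

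**Step 3: allow for correlation.** PFS and OS share events, comorbidity groupings overlap, and pairwise contrasts share groups. The last column comes from 1,500 simulated studies of 580 patients with no true differences, analysed by log-rank test. These were assumed:

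- age shares of 45%, 33% and 22%;
- comorbidity-type prevalences of 4-10% in one scenario and 8-20% in another;
- median time to progression of 31.3 months (protocol section 7, earlier Danish endocrine-sensitive cohort), with an assumed survival after progression;
- censoring between 24 and 84 months.

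The 14-test run placed each patient with comorbidity in a single type. The 44-test run compared age groups with all patients; the 54-test run compared them with each other. Correlation lowers the chance of any false positive but hardly changes the expected number (0.71-0.78 at 14 tests, 2.69-2.96 at 54). The false positives therefore tend to come in clusters.

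**Step 4: age against all patients.** Each subgroup, with share f, is part of its own comparator. If the two are treated as independent, the true standard deviation of the test statistic is the square root of (1/f - 1)/(1/f + 1). At f = 0.20 this is the square root of 4/6 = 0.816. The cut-off of 1.96 then acts as 1.96/0.816 = 2.40, a true level of about 0.016. At f = 0.45 the level is about 0.001. The six age tests add at most about 6 x 0.016 = 0.1 false positives. With them as written, the expected number at 54 tests is 48 x 0.05 = 2.4 plus at most 0.1, or about 2.4 to 2.5 instead of 2.7.

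**The case against.** Both documents disclaim formal hypotheses; they do not rule out every test. Exploratory p-values in an explorative study are a common position, if loosely worded here. The comparisons are listed before the analysis, in SAP 4.2.1 and 4.7.3, so a reader who inferred that the p-values are unplanned would be wrong. Protocol 9.8 lets the SAP modify the plans and define subgroups, so adding the three disease-specific splits is allowed. Protocol 9.4 also gives a reason for using both comorbidity measures: counting weights all conditions equally. Tables 3 and 4 have no p-value column, so selective reporting is a risk and not a planned output.

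A reader might also infer that spurious significant subgroup differences are nearly certain. The documents do not support that. The 94% needs 54 independent tests, no true difference anywhere, and an alpha that the SAP never states. Ten of the 27 contrasts pair comorbidity types that can coexist in one patient, which is a strained reading. Age groups are compared with all patients and not with each other. The protocol's own background cites an observational study of 1,250 patients in which outcomes tended to be worse with a CCI score of 3 or more, and first-line PFS was shorter with cardiac disorders. Some differences may therefore be real.

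All of this stands. It narrows the size of the problem but does not supply the missing rules. Nowhere does the SAP call these p-values nominal or say how to read them, and SAP 4.5 relies on the absence of hypotheses to omit a sample size calculation.

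**Conclusion.** The concern holds as an inconsistency and an under-specification that should be corrected. The SAP orders about 14 to 54 uncorrected PFS and OS tests, plus baseline tests, in a study that both documents call purely descriptive. At an assumed two-sided 0.05 with no true differences, the chance of at least one false positive runs from 51% to 94% if the tests are independent, and from roughly 45% to 82% when correlation is simulated. The simulated figures rest on assumed group shares and prevalences and are approximate. The upper ends use pairwise age tests; the age comparison as written would lower them slightly. Even the most lenient reading leaves close to an even chance of a spurious finding, and the SAP does not say which reading applies. The rank given to the visceral, bone-only and endocrine splits is a labelling fault and not an unauthorised addition.

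**What to change.** **Preferred.** Delete the three test sentences in SAP 4.7.3. Report each subgroup contrast in PFS and OS as a hazard ratio with an unadjusted 95% confidence interval. State that these intervals are exploratory, not corrected for multiplicity and not to be read as tests. That statement is essential: an interval that excludes 1 is essentially p < 0.05, so intervals alone do not remove the multiplicity. The SAP has no hazard ratio analysis at present, only the abbreviation, so this needs a methods sentence and a column in Tables 3 and 4.

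**If p-values are wanted.** Allow one overall test, valid for censored data, per grouping and endpoint, with comorbidity types as present/absent contrasts. State the number, 22, and call the p-values nominal; about 1.1 would fall below 0.05 by chance if nothing differed. Drop the pairwise and baseline tests. Amend the sentences on formal hypotheses in SAP 4.5 and 4.7 and protocol 9.1 to match.

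**Either way.** Label the visceral, bone-only and endocrine rows of Tables 3 and 4 exploratory.

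**Cost.** Fewer p-values to quote, slightly more analysis work, small edits to the SAP text and shells and, if tests are kept, a minor protocol edit. No new data are needed.
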